Objectives	The overall purpose of Phase 1 was to identify brain mechanisms and behavioral markers of placebo analgesia propensity in chronic back pain patients. The markers identified in that phase will now be used in Phase 2 to predict placebo propensity in a separate cohort of chronic back pain patients and in turn, validate the markers' reliability to detect response. An additional objective of Phase 2 is to study the interaction of placebo propensity with active treatment.
Number of Subjects	A total of 340 participants will be enrolled across both phases. Phase 1 will have an expected enrollment of 130 participants to attain 64 completed participants Phase 2 will have an expected enrollment of 210 participants to attain 140 completed participants.
Diagnosis and Main Inclusion Criteria	Chronic back pain (history of low back pain for a minimum of 6 months with or without signs and symptoms of radiculopathy)
Study Product(s), Dose, Route, Regimen	Naproxen, 500mg, po and Omeprazole, 20 mg, po, and matching placebo capsules, all po bid
Duration of administration	6 weeks total for Phase 2 for all study products and treatments
Active Treatment	1 capsule Naproxen (500mg) /1 capsule Omeprazole (20 mg), both oral b.i.d.
Statistical Methodology	Brain activity contrasts are done as a two-way (treatment groups) repeated measures (time: start vs. end) ANOVA (two-way repeated measures-ANOVA). For responders, based on our preliminary results, we anticipate a mean decrease of 2.5 units on a 0-10 scales with an estimated SD of 3. Thus, the estimated Cohen's d effect size across time is an effect size estimate of 0.83.

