responses are across these studies, and how they are sustained for the entire study duration. In all three studies placebo decreases pain by at least 10% within 2-4 weeks and then by an additional 10-30% within 3 months. In **figure 3** (Cox2 NSAID study), placebo treatment decreased CBP pain by >50% in approximately 35% of the group. To unequivocally state that these are placebo responses, it is necessary to have a no-treatment, observation only, control group. Nonetheless, **figure 3** strongly suggests that the placebo effect may be dichotomous, hinting at the notion of two groups: responders and non-responders—this very notion is consistent with our preliminary results. Thus, *if we can identify chronic pain patients who will respond to placebo, then we can potentially decrease the pain in this group by about 30-50%, which would be highly clinically significant.*

Figures 2 and 3 also illustrate an important property of clinical placebo, namely a sustained relief from pain for many weeks. In contrast, experimental placebo studies, by design, only examine very short duration (hours to a few days) effects. Thus, brain circuitry identified for experimental placebo is unlikely to generalize to the clinically observed placebo effects. To our knowledge, using brain circuitry to predict the placebo response in the clinical setting has not been studied outside of our lab.

The current study design specifically addresses aspects of placebo trial design that have received ethical and scientific criticism. A recent review identifies 9 distinct potential sources of bias in placebo effect studies (Hrobjartsson et al., 2011). To circumvent these problems, we rely on randomized controlled trials (RCTs) and within-subject control washout periods, perform all procedures identically across all groups, all preliminary analyses are done blinded, un-blinding occurs only after the completion of data collection, and all primary outcomes are objective brain parameters. By controlling for these factors, the natural, biologically-based propensity for some subjects to be better placebo responders than others can be objectively identified based on the proposed clinical trials.

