2.0 STUDY OBJECTIVES

2.1 Primary and Secondary Objectives

- 2.1.1 To evaluate the interaction between placebo response and active treatment in individuals classified as placebo responders vs non-responders. Individuals in the No Treatment group will be used as a negative control to control for regression to the mean, duration of pain, and other potential confounds.

Hypothesis: Brain functional and anatomical properties between groups after 6 weeks of treatment will identify separate circuitry for placebo analgesia and active treatment analgesia; and these groups will show distinct time courses and magnitudes of analgesia.

- 2.1.2 To test and validate brain imaging and personality parameters identified in Phase 1 that predict the propensity for placebo response and use the results to classify participants into responders vs non-responders before study intervention.

Hypothesis: Brain- and behavioral- based parameters identified as markers of placebo response in the first phase of the study will accurately predict potential responders from non-responders at first scan. The classification before study intervention will closely correspond to the responses observed at the end of treatment period.

- 2.1.3 To identify gender dependence of placebo analgesia propensity and examine brain and personality gender differences that underlie the seeming higher propensity of females for placebo response.

Hypothesis: Sexual dimorphism of the human brain and behavioral/personality differences may have a potential interaction effect and predisposition on placebo propensity. We expect to identify gender-specific biomarkers that are sexually dimorphic with regard to placebo response.

- 2.1.4 Classification of placebo responders versus non-responders for 2.1.2 will be based on Equation 1 below:

$$p = (e^{f(x)}) / (e^{f(x)} + 1)$$

$$f(x) = -3.3586 + 1.6676 * \text{Maia_Emotion} - 0.2127 * \text{Erq_Suppress} + 34.8608 * \text{sign_permutation}$$

where a probability (p) <0.5 = predicts non-responder and a probability (p) ≥0.50 predicts responder.

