These objectives evaluate the notion that placebo effects can be reduced, and perhaps eliminated, from drug trials, by showing that identifiable, separate circuits underlie modulation of pain by each. Additionally, we test the utility of combining a drug treatment with placebo effects. The RCT literature for testing drug efficacy has repeatedly stumbled, in that one study may be successful yet the next fails. One can envision that chance differences in the number of placebo responders and non-responders entering the study may dictate the success of many RCTs. This aim intends to clarify whether placebo responders show medication treatment responses superior to the placebo response, or whether the two independently summate for resultant analgesia. This provides the first effort for dissociating brain activity when pain is modulated by placebo versus medication. As the medication we will study is an NSAID, we assume that its main site of action is the peripheral nervous system and the spinal cord, whereas the placebo effect is obviously mediated through cortical control. Thus, we also dissociate between bottom up and top down modulation of chronic pain. Furthermore, we will begin to identify gender-dependence interactions

on placebo propensity and elucidate sexual dimorphisms in functional and anatomical brain properties in the domain of placebo response.

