participants in each group to do adequate analyses. In other words, we will continue to enroll subjects until we have an adequate number that meet our criteria, using the original randomization list. As addressed previously, we have specific procedures to help minimize subject dropout and missing data. These include the collection of detailed contact information from subjects, maintaining communications logs regarding our contacts with subjects, and a “study identity” that we will use in various communications with subjects (e.g., phone, email, letters). The computer/phone application mentioned previously will also aid us in retaining and tracking our subjects, as well as keeping up with data collection. As subjects drop out of the study, we will document reasons for dropout and address any procedural issues that may be related to dropout. At regular team meetings, we will review the number and percentage of missed assessments. Even with our data-retention plan, there will of course be missing data over time. We will compare subjects with and without missing data to determine whether any subject characteristics are systematically related to missing data. All relationships over time can be analyzed using hierarchical linear modeling (HLM), which provides maximum likelihood estimates for model parameters when data are missing at random. This model is a mixed-effects repeated measures (MMRM) analyses that includes data over time nested within participants. Participant-level variables are included in the model. For this model, participant level variables will be *Maia_Emotion*, *Erq_Suppress*, and *sign_permutation*, just as in the logistic regression model (described above). HLM allows one to model the trajectory of change within subjects, and then determine the effects of covariates (e.g., treatment group) on this trajectory. The exact model tested will be:

$$PAIN_{it} = \beta_{00} + \beta_{01} * MAIA_EMO_i + \beta_{02} * ERQ_SUPP_i + \beta_{03} * SIGN_PER_i + \beta_{10} * DAY_{it} + \beta_{11} * MAIA_EMO_i * DAY_{it} + \beta_{12} * ERQ_SUPP_i * DAY_{it} + \beta_{13} * SIGN_PER_i * DAY_{it} + r_{0i} + r_{1i} * DAY_{it} + e_{it}$$

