In the equation above, $PAIN_{it}$ is the average pain rating for the t th day for the i th participant. r and e terms are error terms. Parameters will be solved for by maximum likelihood estimation. It should be noted that all aspects of this model will be inspected in Phase 2 and alternative models will be examined as needed. This includes models with more complex pain trajectories (e.g., non-linear change over time), and models with additional covariates and/or interactions among covariates

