8.2 Data Analysis Plans

Summary: For brain imaging contrasts, fMRI results show that 20 per group should be adequate given the preliminary results and earlier studies. For DTI and T1 studies our earlier studies indicate that 20/group for within subject contrasts is adequate but may be just at the limit for whole brain contrasts for detecting between group differences. In **Phase 2/Aim 2**, we hypothesize that brain parameters will predict strength of treatment response among the placebo stratified group. The $n = 20$ per group provides adequate sample size for effect sizes of about 1.0.

Given the robust results we have seen already in Phase 1, experimental design and data collection and analysis methods will closely follow the methods we used in Phase 1. To this end, brain imaging data collection details will be identical in Phase 2, all preprocessing and quality control pipelines will remain the same and the same modality comparisons performed in Phase 1 will also be used in Phase 2. Moreover, again we will use a blinded data analysis approach, where for each analysis modality the blinded assessor ([name]) is not involved in any patient interaction throughout the course of the study and will provide three codes for responders and non-responders one of which is the correct result. This forces all analysis to be done across all three codes and the true code is unraveled only when final results are available for all three codes. This approach is more burdensome however it protects against bias and also reveals false positives (for example figure 7 in report). We have employed this strategy for phase 1 results.

Given the results from Phase 1 we have decreased the number of personality related questionnaires that failed to show even borderline relationships with placebo response. In addition, we have extended the washout period to three weeks, as in Phase 1 a one week wash-out was not long enough. Since the two secondary aims of Phase 2 are to show placebo and active drug interaction and persistence of clinical placebo response, we monitor all participants over a 12-week treatment (or no-treatment) period. This design provides us with all the same contrasts that we have available in Phase 1, in addition to looking at placebo propensity and response in relation to active treatment.

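### The pain half of objective 2.1.1 has no stated model or contrast of arm by predicted class, and the DSMP's claim that 17 per group also covers the interaction is unsupported

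*Combined protocol and SAP*

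**What the plan says.** Objective 2.1.1, the first listed, is "To evaluate the interaction between placebo response and active treatment in individuals classified as placebo responders vs non-responders". The text closing section 2.1 asks "whether placebo responders show medication treatment responses superior to the placebo response, or whether the two independently summate for resultant analgesia", and the DSMP (I, Justification of Sample Size) frames the same interaction in terms of change in pain.

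The one pain model written out is in section 4.4. The method is introduced as able to "determine the effects of covariates (e.g., treatment group) on this trajectory. The exact model tested will be" an equation with MAIA_EMO, ERQ_SUPP, SIGN_PER, DAY, the three marker-by-DAY products, and a random intercept and slope. The text then adds that "all aspects of this model will be inspected in Phase 2 and alternative models will be examined as needed", including "models with additional covariates and/or interactions among covariates".

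On power, the DSMP gives 80% at d = 1.0 with 17 per group and says this would let the interaction be detected too. Section 8.1.2 gives power for pre-to-post and two-group comparisons only.

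The status of the interaction varies:
- Section 2.1 lists it first.
- The Study Summary says "An additional objective of Phase 2 is to study the interaction of placebo propensity with active treatment".
- Section 8.2 says "the two secondary aims of Phase 2 are to show placebo and active drug interaction and persistence of clinical placebo response".
- The primary endpoint in 2.3.1 sets placebo response against active response without naming an interaction.
- Section 1.2 says "all primary outcomes are objective brain parameters".

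**The concern.** Section 4.4 presents treatment group as something the model can examine, and the equation that follows leaves it out. If that equation is the pain analysis, none of its coefficients answers whether the drug effect on pain differs between predicted responders and predicted non-responders. The outcome window, baseline window and contrast would then be chosen later, for a question that one section lists first and another calls secondary. A reader of the DSMP would also take the interaction to be as well powered as a simple two-group comparison.

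**Working it through.** **Is the pain contrast stated anywhere?**
- 4.4: no arm, class or arm-by-class term, and no analysis population. Class enters only through its three continuous inputs.
- 4.4, closing text: further covariates and interactions are allowed at discretion. None is named.
- 8.1.1: a group-by-time repeated-measures ANOVA with named post-hoc contrasts, for brain activity.
- 8.2.1: pain time courses may be tested across the four treatment groups. No model, contrast or error rate is given.
- 8.2: methods are to follow Phase 1 closely. Sections 1.2 and 1.3 describe Phase 1 as a placebo-response study, and its report is not among the documents.
- DSMP: names the interaction but gives no equation.

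So the brain part of 2.1.1 has an analysis and the pain part has no fixed one.

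**Power inputs.** d = 1.0 and 17 per group (DSMP). Change of 2.5 with SD 3, so 2.5/3 = 0.83 (8.1.2). 45 randomised per active or placebo cell and 140 completers overall (5.3). Two-sided 0.05 is my assumption for the DSMP figure. Completers per cell: 140 × 3/7 = 60 per arm, and 60/2 = 30 with the roughly 50:50 class split expected in 8.1.1.

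**The plan's own figures.** Two-sample t-test, noncentrality d/√(2/n), 2n − 2 df. For d = 1.0 and n = 17: 1/√(2/17) = 2.92 on 32 df, power 80.7%. The DSMP figure reproduces as a two-group comparison. Section 8.1.2 also reproduces: d = 0.8 with 42 per group, 95.2%; pre-to-post d = 0.8 with n = 23, 95.6%; d = 0.5 with 70 per group, 83.6%.

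**The interaction.** A difference of differences over four equal cells has SE = SD × √(4/n), so noncentrality is δ/√(4/n) on 4n − 4 df, with δ in SD units.

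| n per cell | δ (SD) | noncentrality | power |
|---|---|---|---|
| 17 | 1.0 | 2.06 | 52.8% |
| 8.5 (17 per arm) | 1.0 | 1.46 | 29.2% |
| 30 | 1.0 | 2.74 | 77.5% |
| 30 | 0.83 | 2.27 | 62% |
| 30 | 0.5 | 1.37 | 27.4% |

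A 40,000-run simulation at 17 per cell and 1.0 SD gave 52.9%. For 80% power at 1.0 SD, 32 per cell are needed (128 in four cells). At 17 per cell, 80% is reached at 1.38 SD, with 86% at 1.5 SD and 98% at 2.0 SD.

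**The case against.** **The plan is not silent on pain.** Section 4.4 names hierarchical modelling and treatment group, 8.2.1 names the pain outcomes and the four-group time course, and 8.1.1 expects medication to beat placebo in predicted non-responders. This stands: what is missing is a fixed equation and contrast, not any intention to analyse pain. A reader might go further and infer that objective 2.1.1 has no analysis at all. The documents do not support that, because its hypothesis opens with brain properties and 8.1.1 gives those a model and contrasts.

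**Staff, including the statistician, stay blinded until database lock (5.4).** This limits data-driven choice but does not say which contrast is tested.

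**The DSMP claim may be true.** It gives no interaction size, and from about 1.38 SD upward 17 per cell is enough. So a reader may not conclude that the claim is false, only that it is unsupported. The DSMP's printed effect size of 2.0 does not rescue it: it describes the responders' change, and the stated 3 units with SD 15 give 3/15 = 0.2. On my reading of 8.1.1, if the drug effect is d in predicted non-responders and between 0 and d in predicted responders, the interaction is at most d.

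**Baseline adjustment would raise power.** It may, but the documents do not let the gain be sized. With change SD 3 and equal variances before and after, baseline SD is 3/√(2(1 − ρ)) = 2.54, 3.00 or 3.87 for ρ = 0.3, 0.5 or 0.7. Mean baseline pain must be at least 5/10 to continue (3.2.25, 5.1.7), and on a range of 5 to 10 the SD cannot exceed 2.5. The figures here are therefore unadjusted.

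**Conclusion.** The point holds for the pain part of objective 2.1.1. As written, the 4.4 equation pools the arms and cannot estimate the interaction, and no other section fixes the contrast. This does not depend on any effect size.

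The DSMP's extension of two-group power to the interaction is unsupported: at its own d = 1.0, power is about 53% with 17 per cell, or 29% if 17 is per arm. It would be wrong to infer that the trial was sized on 17, since 5.3 plans 45 per cell and about 30 completers. At 30, power is about 78%, 62% and 27% for 1.0, 0.83 and 0.5 SD. These are illustrations. The 0.83 is borrowed from the responders' change, and all assume two-sided 0.05, equal cells, a common SD, and no gain from covariates or repeated ratings.

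The 80% accuracy criterion in 2.3.2 is not affected. This should be fixed before unblinding.

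**What to change.** 1. **Pain model for 2.1.1, before unblinding.** Specify ARM, STRATUM and ARM × STRATUM in all randomised participants. Use mean pre-treatment app pain over a stated window as covariate (for example visit 1 to visit 2, the reference in section 6.0). Use app pain over one stated treatment window as outcome (for example the 6-week mean, or a defined end-of-treatment window), with the time course as a supporting analysis. Name the contrast: (active − placebo in predicted responders) minus (active − placebo in predicted non-responders), with no treatment as a secondary contrast.
2. **Status.** State whether the interaction is primary or secondary, and reconcile the Study Summary with sections 1.2, 2.1, 2.3.1 and 8.2.
3. **The 4.4 equation.** State its purpose, population and DAY range. If it is meant to support prediction of placebo response (2.1.2), which 4.4 does not say, restrict it to the placebo arm or add arm and arm-by-marker-by-DAY terms.
4. **Power text.** In the DSMP, withdraw the interaction claim or give unadjusted interaction power with its assumptions. Section 8.1.2 needs only a note that it gives no interaction power.

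The cost is text only, since arm, class and app pain are already collected. The downside is a few more fixed effects and a less favourable stated power for the interaction.

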11. PUBLICATIONS -----27

12. REFERENCES -----28

13. SUPPLEMENTS/APPENDICES ----- 32

 I CONSENT FORM TEMPLATE ----- 32

 II LIST OF QUESTIONNAIRES ----- 40

 III AE COLLECTION FORM TEMPLATE ----- 41

 IV DSMP ----- 42

 V STUDY ROSTER -----111

 VI SCHEDULE OF EVALS & ASSESSMENTS ----- 114

 VII BIostatistician CV ----- 117

 VIII LABORATORY PROCEDURES & EVALUATIONS ----- 126

STUDY SCHEMA AND DESIGN

Design Schema for Objective 2 (Phase 2):

We intend to randomize 210 CBP patients into the study with the expectation that 140 will finish successfully. The entire duration of the study will be 12 weeks with an initial 3-week baseline period (visits 1-3), a 6-week treatment period (visits 3-5), and a final 3-week washout period (visits 5-6). During the baseline period eligible **participants will be predicted as placebo responders and non-responders** based upon baseline brain scan results and specific questionnaire answers (properties determined from the results of **Phase 1**) and then classified on that basis. Participants will then be randomized within each classification group (placebo responders and placebo non-responders) at a ratio of 3:3:1 such that 42.5% receive active medication (naproxen/omeprazole, 500/20mg, bid), 42.5% receive matching placebo treatment and 15% no treatment. Brain imaging, self-report questionnaire, and pain/mood rating measurement regimens are shown in **Figure 1**. Pain, mood, and pill ingestion will all be monitored by smart phone for the duration of the study, as well as determined in person at each visit.

[figure not shown]

Figure 1. Experimental schema for Phase 2. Expected changes in pain are shown in solid and dashed horizontal lines. We expect to see different pain outcomes for the various placebo and treatment combination groups. To be noted, we predict that the No Treatment group will have similar pain trajectory as those classified Non-responders and treated with placebo. As well, in the No Treatment group participants will be classified as placebo responders and placebo non-responders, but will not receive any treatment agent, therefore, their pain trajectory will be constant throughout the study.

STUDY SUMMARY

Title	BRAIN MECHANISMS FOR CLINICAL PLACEBO IN CHRONIC PAIN
Short Title	PLACEBO IN CHRONIC PAIN (PICP)
Protocol Number	Grant:
Phase	Grant Phase 2
Methodology	Double blind, randomized (see section 5.4 for more specifics on blinding)
Study Duration	12 weeks
Study Center(s)	Northwestern University

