5.2 Procedures During Treatment

5.2.1 Schedule of Events for all participants

- Visit 1 (week-3): Consent, screening, and baseline pain/mood monitoring (45 min). Participants will complete the informed consent process and are evaluated for initial inclusion/exclusion criteria, and they will be asked to assess current back pain intensity on a VAS scale. They will be asked to assess current back pain intensity on a VAS scale (0-10mm, no pain to worst possible pain). A medical/pain history and physical examination including vitals will be completed. Blood will be drawn for an initial screen to obtain a complete blood count, chemistry panel, and liver function tests (data reviewed by [name]). Participants will be asked to discontinue their current pain medications ~14 days (2 weeks) prior to their first scanning visit. Participants will receive acetaminophen (rescue medication) at the time of the visit. They will be shown how to use the smart phone/computer application (and given a phone if necessary), and they will be instructed to rate their pain and mood with the app two times a day for the duration of the study. Participants will complete questionnaires and return within 2 weeks for the first MR imaging scans. This length of time is adequate to allow scheduling and permit flexibility for subjects' preferences, and to ensure that pain levels persist at or above 5/10 VAS collected from the pain rating app and that participants do not significantly respond (>20% decrease) to the acetaminophen rescue medication. In addition, the entry interview will be conducted at this visit.

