8.1.2 Sample Size and Accrual

Statistical power can be estimated based on the Cohen's d effect sizes for differences in pain with 6 weeks of treatment. For responders, based on our preliminary results, we anticipate a mean decrease of 2.5 units on a 0-10 scales with an estimated SD of 3, which results in an effect size estimate of 0.83. In non-responders, the mean decrease in pain is negligible and we do not expect to have enough power to detect this.

Power analyses in G*Power 3.1.3 indicated that we will have ample power to detect pre-to-post changes within a group; with an estimated effect size of $d = 0.8$, power would exceed 95% with a sample of 23 participants. In terms of a between-group comparison, assuming an effect size estimate of $d = 0.8$ across groups, power would exceed 95% for a sample size of $n = 42$ per group. Thus, the total sample size of 210 would provide for adequate power, even accounting for

potential dropout and/or lower-than-expected effect sizes. Assuming that we recruited 70 participants per group, for example, would mean that we could detect between-group effects as small as $d = 0.5$ with power exceeding 80%.

Power analysis for gender: The preliminary gender analyses from phase 1 subjects provide the means to calculate the power necessary for detecting gender effects in placebo propensity. The original sample sizes from phase 1 were based on treating gender and age as covariates of no interest. Based on an anticipated medium-sized effect using Cohen's conventions (Cohen, 1992), calculations in `chi2power` in Stata indicated that for $n=82$ and for $\alpha = 0.05$ we obtain power = 0.31. Instead if we double the number of subjects then we reach adequate detection power: assuming that males have 30% while females 50% placebo incidence rate, for $\alpha = 0.05$ and $n=160$ we obtain just adequate power = 0.74. Therefore all data from phase 1 and 2 will be combined to assess effect of gender on placebo response.

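### The stated longitudinal pain model fits one straight DAY slope across baseline, treatment and washout, so its marker x DAY terms mix response, speed of onset and persistence

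*Combined protocol and SAP*

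**What the plan says.** The Study Schema sets out a 12-week study "with an initial 3-week baseline period (visits 1-3), a 6-week treatment period (visits 3-5), and a final 3-week washout period (visits 5-6"). At visit 1 (section 5.2.1) participants are told how to use the app and "they will be instructed to rate their pain and mood with the app two times a day for the duration of the study".

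Section 4.4 presents hierarchical linear modelling as the way to analyse change over time with missing data, and leads into the equation with "determine the effects of covariates (e.g., treatment group) on this trajectory. The exact model tested will be". The outcome "is the average pain rating for the t th day for the i th participant". The fixed effects are an intercept, the three markers (MAIA emotion, ERQ suppression, sign permutation), DAY, and each marker times DAY. The random effects are an intercept and a DAY slope. No term identifies the study period, and no sentence says which days DAY covers.

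Section 4.4 then says that the model will be inspected and alternatives examined as needed: "This includes models with more complex pain trajectories (e.g., non-linear change over time), and models with additional covariates and/or interactions among covariates". No form, trigger or order is given.

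Section 8.2 names persistence of the clinical placebo response as a secondary aim, and says the one-week washout used in Phase 1 was too short.

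**The concern.** Pain is expected to fall on treatment and may return in washout. A straight line has one direction, so it cannot describe a fall followed by a return. It summarises such a profile by how far the end of the study lies below the start, and that depends heavily on what happens in washout.

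The marker x DAY coefficients are the equation's test of whether the markers predict the pain trajectory. A marker of prompt, reversible response could show little in them, and a marker of slow reversal could show a lot. A reader of the results could not tell response from persistence, although persistence is one of the trial's aims.

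**Working it through.** **Inputs.** Periods of 21, 42 and 21 days (Study Schema), numbered 1 to 84, so treatment is days 22 to 63. Effect 2.5 units with SD 3 (section 8.1.2: "we anticipate a mean decrease of 2.5 units on a 0-10 scales with an estimated SD of 3"; 2.5/3 = 0.83, as stated there). Section 8.1.2 also gives power above 95% for d = 0.8 with 42 per group. The noncentral t, two-sided 0.05, gives 95.2%, so that figure reproduces and is not in dispute. The plan gives no power for the DAY slope. Assumptions here: DAY covers all 84 days, data are complete, and one rating a day enters.

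**Slope.** For an effect of -2.5 x f(t), with f between 0 and 1, the least-squares slope is

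b = -2.5 x Σ(t - 42.5) f(t) / Σ(t - 42.5)²

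The denominator is 84 x (84² - 1)/12 = 49,385. The fitted change from day 1 to day 84 is 83b.

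- Immediate onset and offset: treatment days average (22 + 63)/2 = 42.5, the study midpoint, so the sum is 0 and b = 0.
- No reversal: washout days 64 to 84 average 74, so the sum is 21 x (74 - 42.5) = 661.5 and b = -2.5 x 661.5/49,385 = -0.0335.
- Linear onset and offset over 7 days each: the sum is 126 and b = -0.00638. Over 14 days each: the sum is 273 and b = -0.01382.

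The last column sets beside these the treatment-period mean minus the baseline mean for the same profile. For 7-day ramps that is -2.5 x 39/42. For 14-day ramps it is -2.5 x 35.5/42.

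| Profile of the same 2.5-unit fall | Fitted change, 83b | Treatment minus baseline |
|---|---|---|
| Immediate on, immediate off | 0.00 | -2.50 |
| 7-day ramps | -0.53 | -2.32 |
| 14-day ramps | -1.15 | -2.11 |
| Immediate on, no reversal | -2.78 | -2.50 |

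**Visit windows.** Section 5.5 allows ±5 days. With periods of 16, 42 and 26 days, treatment is centred 5 days early: the sum is 42 x (-5) = -210, b = +0.01063 and the fitted change is +0.88. With 26, 42 and 16 days it is -0.88. The sign then follows scheduling.

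**Range of DAY.** For the immediate step, the fitted change over the span is 0 with treatment days only, -3.28 with baseline plus treatment, and +3.28 with treatment plus washout.

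**Power.** A simulation with 60 patients in two equal marker groups, mean falls of 2.5 and 0, person-level SD of change 3, daily SD 1.2, complete data, two-sided 0.05 and 4,000 runs. It compares a t test on per-person slopes with one on the treatment-minus-baseline contrast. The 60 patients, the two groups and the daily SD are assumptions.

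| Profile | Slope | Phase contrast |
|---|---|---|
| Immediate on and off | 5% | 88% |
| 7-day ramps | 73% | 88% |
| 14-day ramps | 86% | 88% |
| No reversal | 88% | 89% |

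**Check of the remedy.** In a random intercept and slope model with 140 simulated participants, a binary marker, an immediate step and assumed variances, marker x DAY averaged -0.002 units over 84 days, with 3% rejection. Adding an on-treatment indicator and its marker interaction returned -2.50, the true value.

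**The case against.** A reader might infer that any effect that appears on treatment and reverses in washout has an expected slope of zero. The documents do not support that. Zero needs same-day onset, same-day full offset, complete data and exact periods. Section 1.2 describes placebo responses building over weeks, section 8.2 reports slow offset in Phase 1, section 5.3 expects about 33% attrition and section 5.5 allows flexible visits. In a simulation with one third dropping out evenly from the start of treatment (assumed variances), a step effect gave about -0.93 units over 84 days. With two-week ramps the test loses little power. This limits the loss of detection. It does not make the slope an estimate of response, since its size then depends on onset, offset, scheduling and who leaves.

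A reader might also infer that a good marker would be judged useless. That fails too. Section 2.3.2 validates the markers by at least 80% accuracy in separating responders from non-responders, section 8.2.6 makes logistic regression the primary test for the questionnaires, and section 8.2.7 tests the Phase 1 classifier. No endpoint or power statement rests on the section 4.4 model.

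Two further points are fair. The range of DAY is not stated, so the 12-week reading is an inference from ratings being collected throughout. And section 4.4 does anticipate non-linear change. But it names no alternative, so the shape of time would be chosen after the data are seen, and the model called exact stays as written.

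**Conclusion.** The point stands in a limited form and the plan should be amended. The stated model confounds response to treatment with speed of onset and persistence into washout: one and the same 2.5-unit fall gives a fitted change anywhere from 0 to -2.78, and a step effect gives about ±0.9 when the periods shift by 5 days. The slope figures rest on DAY covering all 84 days with complete data. The power figures rest also on the assumed 60 patients and variances, and show serious loss only when the effect is prompt and reversible. What is affected is the longitudinal pain model and the persistence aim. The 80% accuracy criterion and the logistic regression are untouched. The absence of treatment arm from the same equation is a separate matter.

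**What to change.** In section 4.4:

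- State which days enter the model.
- Replace linear DAY with two indicators set by actual visit dates: TREAT (visits 3 to 5) and WASH (visits 5 to 6), with baseline as reference. Piecewise-linear time with knots at visits 3 and 5 is an acceptable alternative; choose one in advance.
- Include each marker x TREAT and marker x WASH, with a random intercept and a random TREAT effect. As marker x WASH is itself tested, add a random WASH effect if it can be estimated.
- Name marker x TREAT as the test of response and marker x WASH as the test of persistence.
- Keep other time shapes as labelled sensitivity analyses, fixed before unblinding.

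The cost is wording and a few parameters: with the indicators, fixed effects go from 8 to 12 (intercept, 3 markers, 2 phases, 6 interactions). No new data are needed.
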